## 9.3 Data Analyses Plans

The local control rate and the proportion of patients whose tumors did not grow will be estimated along with the corresponding 95% confidence interval using the exact binomial method. The frequency of the adverse events associated with the administration of SABR to SRMs will be computed. Descriptive statistics such as mean, range, and 95% confidence interval will be computed for the growth rate of SRMs after SABR treatment, and the changes in kidney function, creatinine levels, renal perfusion and GFR after SABR treatment. Descriptive statistics will be also computed for radiographic changes of the SRM after SABR treatment, including tumor viability, %enhancement, necrosis, T2 signal, and tumor cellularity with diffusion-weighted imaging.

Kaplan-Meier method will be used to estimate the time to progression (TTP) of disease from the first SABR treatment, progression free survival (PFS), and overall survival (OS). Exploratory data analysis will be conducted to assess the cytokine changes brought on by SABR to SRM and to evaluate generation of any immune response specific to tumor cells.

We will compute the following characteristics of CT and MRI acquired prior to the treatment and follow-up scan: intensity features such as minimum, maximum, mean, standard deviation, median, skewness, kurtosis; texture features such as energy, entropy, correlation, inertia, cluster shade; geometry features such as volume, major axis length, minor axis length, eccentricity, elongation, roundness. The ability of each feature to predict treatment response will be quantified by the area under the receiver operating characteristic curve (AUC). An AUC of <0.7 will be considered to have low accuracy, 0.7-0.9 to have moderate accuracy, and >0.9 to have high accuracy.

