Radiation induced renal complications can be slow and non-inflammatory. The extent of radiation induced kidney damage is related to the volume of renal parenchyma receiving radiotherapy, total dose given to the kidney, dose per treatment, and other underlying medical conditions such as diabetes and hypertension. Acute radiation nephritis can be seen months after exposure to radiotherapy [48]. The clinical symptoms related to acute radiation nephritis include hypertension, edema, proteinuria, anemia, and uremia. In standard fractionated treatment to both kidneys about 50% of the patients will develop the clinical manifestation described above a dose of 23 Gy [49]. Among the clinical symptoms, the development of hypertension is the most important prognostic sign correlated with severe morbidity and death. However, when 50% or less of a single kidney is irradiated to a high dose (>26 Gy), clinical radiation induced nephropathy is rare [49].

In this phase II trial, the volume of high dose radiotherapy (>10 Gy) will be restricted to <50% of the entire kidney. The current study will also implement fractionated stereotactic radiosurgery to treat a unilateral kidney tumor. Fractionated radiotherapy is advocated to further reduce the potential toxicity arising from a large single fraction regimen. In fact, fractionated radiotherapy has been the standard treatment for many tumors in variety of locations to reduce the toxicity associated with radiotherapy. A fractionated stereotactic regimen has the potential to reduce the normal tissue toxicity that often accompanies radiotherapy.

Successful implementation of stereotactic radiosurgery of renal tumors may become an effective and the least invasive treatment modality. This study will refine the current understanding of the image guided conformal therapy to the kidney using stereotactic body radiotherapy.

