### **2.4.2 Secondary Endpoints:**

- 2.4.2.1 Adverse Events: Acute and late adverse events will be assessed using NCI's CTCAE v4.0 toxicity criteria and RTOG/EORTC criteria (Appendix A and B).
- 2.4.2.2 Growth Rate: Growth of the longest diameter of the SRMs after SABR treatment will be compared to baseline and expressed as growth rate of cm/year.
- 2.4.2.3 Loco-regional and systemic progression: Loco-regional and systemic progressive disease will be defined based on local, regional and systemic progression as defined by AJCC (7th edition) kidney cancer staging and any stage >T1a (>4cm) constitutes a progression.
- 2.4.2.4 Kidney function: To assess kidney function creatinine levels and renal perfusion scan will be performed at baseline and periodically after SABR (See section 5).
- 2.4.2.5 Radiographic changes: Radiographic changes of the SRM after SABR treatment will be assessed using MRI interpretation by a radiologist.
- 2.4.2.6 Tumor Growth, Local failure and Indeterminate Disease Response as defined in section 6.1.4

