**4.11 Duration of Follow Up**

Subjects will be followed for 2-5 years with MRI scans every 6 months for the first year and if there is no growth then every six months subsequently; if there is evidence of growth, frequency will be determined by physician.

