**4.13 Subject Replacement**

The following are criteria for subject replacement: 1) If the subjects decide to withdraw from the study without finishing the course of SABR, 2) if the subjects decide to withdraw from the study or lost to follow up (for reasons of death from other causes, moving to other state etc.) or refuse follow up scans leading to <3 follow-up scans or <1 year of follow up, 3) if the subjects become unable to undergo an MRI or contrast enhanced CT scan with <1 year of follow up.

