### **6.3 Safety/tolerability**

Analyses will be performed for all subjects having received at least one fraction of radiation of study intervention. The study will use the CTCAE version 4.0 for reporting of non-hematologic adverse events (<http://ctep.cancer.gov/reporting/ctc.html>) and modified criteria for hematologic adverse events (Appendix #/letter).

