### **Late Adverse Events**

Adverse effects occurring in the time period from the [end of acute monitoring](#), to 3 years post treatment for progression or death (whichever comes first), will be defined as late adverse events. These events will include all adverse events reported directly to a member of the study team and will be captured, assessed, graded and reported as appropriate.

In addition, the study team will review encounters in a select specialty category relevant to study endpoints. These select specialties include hospitalizations, medical oncology, and radiation oncology records and will be limited in scope based on categorization of events ([GU/GI](#)) and also the type of records that will be queried (hospitalizations, [medical oncology, and radiation oncology](#)).

An adverse event is defined as any untoward or unfavorable medical occurrence in a human research study participant, including any abnormal sign (for example, abnormal physical exam or laboratory finding), symptom, clinical event, or disease, temporarily associated with the subject's participation in the research, whether or not it is considered related to the subject's participation in the research.

Adverse events encompass clinical, physical and psychological harms. Adverse events occur most commonly in the context of biomedical research, although on occasion, they can occur in the context of social and behavioral research. Adverse events may be expected or unexpected.

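### Late adverse events are summarised only as a crude frequency, which can understate the 3-year risk when treated subjects leave early or are followed for less than 3 years

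*Protocol*

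**What the plan says.** Section 9.3 assigns a method to each endpoint. Local control gets an exact binomial estimate with a 95% interval. For the time-to-event outcomes, "Kaplan-Meier method will be used to estimate the time to progression (TTP) of disease from the first SABR treatment", and the same sentence covers progression-free and overall survival. For toxicity the whole plan is: "The frequency of the adverse events associated with the administration of SABR to SRMs will be computed". It sets no time horizon or denominator and does not separate acute from late events.

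Five other places bear on this:

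- **Endpoint (2.4.2).** Late toxicity is a named secondary endpoint: "Acute and late adverse events will be assessed using NCI's CTCAE v4.0 toxicity criteria and RTOG/EORTC criteria".
- **Window (7.2.1).** The acute period runs to 12 weeks after treatment. The late period runs from there "to 3 years post treatment for progression or death (whichever comes first), will be defined as late adverse events".
- **Population (6.3, consistent with 4.9 and 6.1.1).** "Analyses will be performed for all subjects having received at least one fraction of radiation of study intervention". No minimum follow-up applies.
- **Replacement (4.13).** Grounds for replacement include withdrawal, loss to follow-up or refusal of scans "leading to <3 follow-up scans or <1 year of follow up".
- **Follow-up length.** Section 4.11 says: "Subjects will be followed for 2-5 years with MRI scans every 6 months for the first year". Section 5.3 instead schedules six-monthly visits for five years for every subject, each with a toxicity evaluation. Subjects with progressive disease or a new primary move to survival-only follow-up.

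**The concern.** A crude proportion is adequate for acute events, because nearly every treated subject passes through a 12-week window. Late events are different. A treated subject who leaves at 6 months stays in the denominator but contributes little time in which a late event could be seen. If the proportion is then read as a 3-year risk, that subject counts as event-free for time that nobody observed. The error runs one way: in expectation the crude figure cannot exceed the 3-year risk, and it can fall below it.

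The protocol allows for censoring in three endpoints but not in a fourth that depends on time in the same way. Describing adverse events is the first secondary objective, and section 1.3 warns that "Radiation induced renal complications can be slow and non-inflammatory". The later the onset, the more a crude proportion loses to short follow-up. The late toxicity figure will be read by people weighing SABR for patients who would otherwise be under active surveillance.

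**Working it through.** The protocol states no late toxicity rate, so there is no figure of its own to reproduce. The true rate, the follow-up mix, the number of replaced subjects and the hazard shape below are all assumptions. From the documents come the 16 subjects, the 12-week start and 3-year end of the late window, the 2-5 year rule, the five-year schedule and replacement before one year.

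**Formula.** Let p be the true 3-year cumulative incidence. A subject observed for t years (t at most 3) has an event with probability 1 − exp(−H(t)). The expected crude frequency is the mean of this over all treated subjects.

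**Case A: everyone observed for at least 3 years.** Each subject contributes p, so crude equals p and there is no bias.

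**Case B: follow-up even over 2-5 years, no replacements.** The hazard is constant from week 12. Two thirds of subjects cover the full window; one third are spread evenly over 2-3 years. For p = 20%:

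- λ = −ln(0.8)/(3 − 12/52) = 0.0806 per year.
- Mean probability in the 2-3 year group: 16.7%.
- Crude = (2/3)(20%) + (1/3)(16.7%) = 18.9%.

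For p = 10% and 30% the crude figures are 9.4% and 28.4%. The shortfall is 5-6% relative, or 0.1 to 0.25 patients of 16. With a hazard rising linearly from first treatment, the crude figure for p = 20% is 18.2%.

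**Case C: everyone stopped at exactly 2 years.** This is the extreme under section 4.11 before withdrawals. With the constant hazard of Case B, crude is 6.5%, 13.3% and 20.4% for p = 10%, 20% and 30%.

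**Case D: eight subjects observed 2 years, eight observed 3 years, and three replaced subjects who were treated but left at 6 months.** Here H(t) = −ln(1 − p)(t/3)^k from first treatment, with p = 20%.

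| | 6 months | 2 years | 3 years | Crude, 16 subjects (no replacements) | Crude, all 19 |
|---|---|---|---|---|---|
| k = 1 (constant) | 3.7% | 13.8% | 20% | 16.9% | 14.8% |
| k = 2 (rising) | 0.6% | 9.4% | 20% | 14.7% | 12.5% |

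For k = 1 over 19: (8 × 0.138 + 8 × 0.200 + 3 × 0.037)/19 = 0.148. The shortfall over all 19 is 26% (k = 1) to 38% (k = 2) relative. If all 16 reach 3 years and only the three replaced subjects leave early, crude is 17.4% (k = 1) or 16.9% (k = 2).

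**Does a censoring-aware estimate correct it?** In 20,000 simulated trials of 16 subjects with p = 20% and no competing events, follow-up even over 2-5 years gave a mean crude proportion of 18.9% (SD 9.7 points). One minus Kaplan-Meier gave 20.0% (SD 10.4 points). With follow-up even over 2-3 years, the means were 16.7% and 19.4%, with SDs of 9.4 and 13.2 points. Most of the bias goes, at the price of more variance.

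**Scale.** The exact 95% interval for 2 events in 16 is 1.6% to 38.3%.

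**The case against.** The strongest reply is that section 9.3 contains a general sentence, not a rule. It does not say that late events will be divided by all treated subjects and read at 3 years, and denominators and censoring for safety tables commonly go in a statistical analysis plan, which is not at hand. That stands as far as it goes: silence on those details is no fault. But the protocol does choose an estimator endpoint by endpoint, and for this one it chose a frequency.

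Three stronger readings are tempting, and the documents do not support them.

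- **That follow-up differs greatly and late toxicity is bound to be understated.** The late window closes at 3 years, so under the 2-5 year rule subjects differ inside it by at most one year, early exits aside. Under section 5.3 they differ only through such exits. The bias is conditional and may be zero.
- **That the window ending at progression or death adds to the bias.** If these are competing events, such subjects properly stay in the denominator as not having had a late event first. Without censoring, cumulative incidence then equals the crude proportion. Only true loss of observation matters: withdrawal, loss to follow-up, short follow-up, or a new primary that moves a subject to survival-only visits without closing the late window.
- **That renal injury is the protocol's main safety concern and is covered only by this frequency.** Section 1.3 says renal complications can be slow, but also that nephropathy is rare when half or less of one kidney is irradiated. Section 9.3 separately summarises kidney function, creatinine, perfusion and GFR with 95% intervals.

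It is also fair that no test, threshold or stopping rule uses the late rate, and that with 16 subjects sampling error exceeds the bias in most of these cases. An interval around a crude proportion does not remove the bias, however.

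**Conclusion.** The point holds in conditional form. A crude frequency of late events over all treated subjects cannot, in expectation, overstate the 3-year risk. It can understate it when subjects are lost, replaced before one year or followed for only 2 years. If all complete the five-year schedule, there is nothing to correct.

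For an assumed true 20%, the crude figure runs from about 19% (even 2-5 year follow-up, no replacements) to about 12-15% (half stopped at 2 years plus three early replacements). The lower end also needs a rising hazard, and none of these mixes is in the protocol. This is a modest reporting weakness in a descriptive secondary endpoint, worth correcting because the remedy is cheap. The disagreement between sections 4.11 and 5.3 on follow-up length is a separate, plain inconsistency, and it decides how large the bias could be.

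**What to change.** In section 9.3, keep simple frequencies for acute events. For late events add the cumulative incidence at 1, 2 and 3 years, with 95% confidence intervals and the number at risk at each time. Include every subject who received at least one fraction, censor at the last toxicity evaluation, and treat death and progression as competing events, in line with the window in section 7.2.1.

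Reconcile the follow-up lengths in section 4.11 (2-5 years) and section 5.3 (five years) with each other and with the 3-year late window, so that the intended observation time is clear.

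The cost is a sentence or two in section 9.3 and a little more analysis. No new visits are needed, since toxicity is already evaluated at six-monthly visits; event and last-evaluation dates must be available. Intervals will be wide with 16 patients, and the estimate assumes that subjects who leave early have the same late risk as those who stay.

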Many surrogate markers for activated and proliferating lymphocytes have been described. Some of these markers include CD25, CD71, CD45RO, CD107a, CD54, CD69, Ki67 and ICOS/CD278 [82-85]. These markers are easily measured with antibodies specific for the markers that are tagged with a fluorophore utilizing FACS analysis. Also using FACS, activation markers on other immune cells such as CD80 and CD 86 on DCs, and inhibitory markers on monocytes such as PD-1 can be measured as surrogates of immune activation or inhibition. These measurements from PBMCs collected from patients before and after treatment will give us further information regarding the intensity of the immune response. Additionally, PD-L1, the ligand of PD-1, often expressed in tumor cells, can be quantified from patient pre-treatment tumor biopsy.

The relative levels of different monocyte subpopulations in the tumor biopsy sample after treatment as well as in the peripheral circulation often dictate the overall outcome of an immune response, and has been reported in previous immunotherapy trials [86]. Exploration of possible mechanisms of treatment failure can be explored from this analysis as well. Therefore, different subpopulation of monocytes and lymphocytes will be quantified in patient PBMCs (and in tumor biopsy samples where applicable) collected before and after treatment utilizing markers specific for those cells.

Many studies have suggested that imaging characteristics of tumor may be used to predict treatment outcome of radiation therapy for various tumors, such as lung [87], prostate[88], cervical[89]. By analyzing CT and MRI images on patient enrolled in this trial, we plan to explore whether image characteristics of CT and MRI acquired prior to the SBAR treatment, such as intensity features, texture features and geometry features, are correlated with the treatment outcome of SABR for RCC. Through analysis of the change of these image characteristics in the follow-up scans, we will also explore whether the change of these features can be used for early prediction of SABR treatment response.

Multiple clinical and pre-clinical studies have demonstrated the dependence of tumor radiation resistance with tumor hypoxia, including those performed in our institution [90-94]. Using a combination of blood oxygen level dependent (BOLD) and tissue Oxygen Level Dependent

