## **2.4 Endpoints**

### **2.4.1 Primary Endpoint:**

Local control of the SRMs will be defined as <4mm increase in the longest tumor diameter compared to pre-treatment scan on an MRI or contrast-enhanced CT scan in the setting of no radiographic or pathologic evidence of viable tumor.

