## 9.2 Sample Size and Accrual

There is no reliable historic information on local control rate of SABR for primary RCC since the retrospective studies have used a wide range of SABR dose fractions and varying definitions of local failure. From the retrospective studies and one phase I trial, we found three local failures out of 34 patients (section 1.3). Thus, it is expected that the local control rate will be at least 90% in this trial. With a sample size of 16 patients, the standard error of local control rate will be at most 7.5% with a 95% confidence interval of 15%, since the local control rate is expected to be at least 90%.

A sample size of 16 patients in this single-arm phase II trial will have more than 90% power to detect the difference between 100% pre-treatment tumor growth and 50% post-treatment tumor growth using a two-sided binomial test with a 0.05 significance level. With the sample size of 16 patients in this single-arm phase II trial, a single group t-test with a two-sided 0.10 significance level will have 80% power to detect the difference between a pre-treatment tumor growth rate of 0.4 cm/year and a post-treatment tumor growth rate of 0.16 cm/year (a 60% reduction), assuming that the standard deviation is 0.36 cm/year. The power calculations were conducted using the software PASS 12.

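### Section 9.3 labels imaging features by point AUC alone, though local control in 16 patients would leave about 1.6 failures or fewer, and it does not keep follow-up size features apart from the response they predict

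*Protocol*

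**What the plan says.** Section 9.3 lists seven intensity features, five texture features and six geometry features, the last being "geometry features such as volume, major axis length, minor axis length, eccentricity, elongation, roundness". They are computed on CT and MRI from before treatment and from follow-up. Each feature's ability to predict treatment response is measured by the AUC, and the grading rule is: "An AUC of <0.7 will be considered to have low accuracy, 0.7-0.9 to have moderate accuracy, and >0.9 to have high accuracy". The rule acts on the AUC estimate itself.

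The analysis serves exploratory objective 2.3.2, and exploratory endpoint 2.4.3.2 names the AUC as its measure. Section 1.4.1 gives the purpose of the follow-up features: to explore "whether the change of these features can be used for early prediction of SABR treatment response".

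Two other places bear on the rule. Section 9.2 sets the sample size at 16 and states that "it is expected that the local control rate will be at least 90% in this trial". Section 2.4.1 defines local control partly by size, as "<4mm increase in the longest tumor diameter compared to pre-treatment scan", together with no radiographic or pathologic evidence of viable tumor. Section 6.1.4.1 uses the same two components for local control and local failure, and lists several other response categories beside them.

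**The concern.** An AUC compares patients who fail with patients who do not. When the failures number one or two, the AUC can take few values, and a feature unrelated to outcome can land above 0.9 by chance. A fixed label on the point estimate turns that chance into a statement of high accuracy, and the exercise is repeated over at least 18 features. With no failures the AUC does not exist, and section 9.3 does not say what is then reported.

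The second issue is overlap. Tumor volume and axis lengths on a follow-up scan measure much the same thing as the change in longest diameter that helps decide response. Section 9.3 does not say which follow-up scan supplies the features, or that it must come before the response assessment. If it is the scan that decides response, part of the apparent prediction is built in.

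At stake is the answer to objective 2.3.2: which features, if any, are worth taking into a later study.

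**Working it through.** **Inputs.** N = 16 and local control of at least 90% (section 9.2); three failures in 34 earlier patients (section 9.2); 7 + 5 + 6 = 18 named features and the 0.9 cut-off (section 9.3). Assumption: treatment response is read as local control, the primary endpoint and the response category for which section 9.2 gives an expected rate.

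**The plan's own figure.** Section 9.2 states: "With a sample size of 16 patients, the standard error of local control rate will be at most 7.5% with a 95% confidence interval of" (the figure it then gives is 15%). Check: sqrt(0.9 × 0.1 / 16) = 0.075, and 2 × 0.075 = 0.15. This reproduces, with the 15% as a half-width. No precision is stated for the AUC analysis.

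**Number of failures.** Expected: 16 × 0.10 = 1.6, or 16 × 3/34 = 1.4. Under Binomial(16, 0.10): P(0) = 0.185, P(1) = 0.329, P(2) = 0.275, P(3) = 0.142, P(4 or more) = 0.069. So P(2 or fewer) = 0.79. At 3/34, P(0) = 0.228.

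**Chance that one noise feature exceeds 0.9.** For m failures, AUC = U / [m(16 − m)], with U the Mann-Whitney count. With no predictive value, every allocation of ranks to the failures is equally likely.
- m = 1: AUC is a multiple of 1/15; only 14/15 and 15/15 exceed 0.9. Probability 2/16 = 12.5%.
- m = 2: U must be at least 26 of 28. Probability 4/120 = 3.3%.
- m = 3: U must be at least 36 of 39. Probability 7/560 = 1.25%.

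**At least one of 18 noise features above 0.9.** If independent, 1 − (1 − p)^18:
- m = 1: 1 − 0.875^18 = 0.910
- m = 2: 1 − 0.9667^18 = 0.457
- m = 3: 1 − 0.9875^18 = 0.203

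Weighting by the binomial probabilities, with no failures contributing nothing: 0.329 × 0.910 + 0.275 × 0.457 + 0.142 × 0.203 + about 0.007 for four or more = 0.300 + 0.125 + 0.029 + 0.007 = **0.46**.

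The features are not independent (volume and the axis lengths, for instance). The documents give no correlation, so a range is assumed. Simulating 18 equicorrelated normal features:

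| Pairwise correlation | m = 1 | m = 2 | Averaged over failures |
|---|---|---|---|
| 0 | 91% | 46% | 46% |
| 0.5 | 59% | 27% | 29% |
| 0.8 | 39% | 16% | 18% |

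More scan times or modalities raise these. With 36 independent features (two scan times) the average is 0.329 × 0.992 + 0.275 × 0.705 + 0.142 × 0.364 + about 0.013 = 0.59.

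**Precision.** The Hanley-McNeil standard error of an AUC of 0.9 is 0.21 with one failure and 0.15 with two. The gap between the top and bottom labels is 0.9 − 0.7 = 0.2, so the data cannot separate them.

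**Overlap, by comparing sections.** Sections 2.4.1 and 6.1.4.1 judge growth by longest diameter. Three of the six geometry features in section 9.3 (volume, major axis, minor axis) are direct size measures. Scans are six-monthly (section 5.3) and the endpoint is read at one year or later (section 9.1), so an earlier scan exists; section 9.3 does not require its use.

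**The case against.** The strongest reply is that the analysis is exploratory. The label triggers no decision, stopping rule or change of treatment, and leaves the primary estimate untouched. Confidence intervals and multiplicity control for exploratory AUCs are often placed in a statistical analysis plan, which is not at hand. This stands as a limit on importance, and the absence of those items is not the point here. The point is the cut-off on the point estimate and the unrestricted follow-up features, both of which the protocol itself fixes.

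It is also fair to say that the failure count depends on reading treatment response as local control. Sections 2.3.2, 2.4.3.2 and 9.3 do not say so, and for a RECIST split or the indeterminate category the protocol states no expected rate. The figures hold only under that reading.

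A reader might infer more than the documents support, in three ways:
- That noise features are bound to be reported as predictors, citing 91%. That figure is conditional on exactly one failure, which has probability 33%, and on independent features.
- That chance passes are twice as frequent (25% with one failure) because an AUC below 0.1 predicts equally well in reverse. The written rule puts such a value in the low class.
- That the analysis is wholly circular. Pre-treatment features are not circular, local control also requires absence of viable tumor, and section 1.4.1 aims the follow-up changes at early prediction. The overlap is partial and depends on which scan is used.

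**Conclusion.** The point holds in limited form. With local control as the response and a true failure rate of 10%, the rule in section 9.3 cannot be applied in 19% of trials. Over all trials it gives at least one of 18 uninformative features the top label with probability about 46% under independence, or about 18-29% at an assumed correlation of 0.5-0.8. Mislabelling is therefore a material risk rather than a certainty, and using more scan times or both modalities increases it. Separately, follow-up size features can partly restate the response unless they come from an earlier scan, which the section does not require. The consequence is confined to the interpretation of exploratory objective 2.3.2; the primary conclusion is unaffected.

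**What to change.** Amend section 9.3 and keep the AUC, as endpoint 2.4.3.2 specifies:

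1. Name local control as the response to be predicted.
2. Report each AUC with an exact or permutation-based confidence interval and the number of failures behind it.
3. Drop the low, moderate and high labels, or apply them only to the lower confidence limit.
4. Use follow-up features only from a scan earlier than those that define response, for example the six-month scan, and exclude size measures taken from the response-defining scan.
5. State that no AUC is reported if there are no failures.

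Replacing the AUC by a correlation with growth rate or change in diameter would avoid the sparse failures, but it is not advised: it changes endpoint 2.4.3.2, drops viability from the response and increases the overlap with the size features.

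The cost is a wording change with no new data. The downside is that few or no features will be called accurate, which is what 16 patients can support.
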